# 1 INTRODUCTION

# 1.1 RATIONALE

To determine if "high risk" surgical incisions develop healing complications within 21 days of surgery. High risk is defined as a standard incision in the "high risk patient" (diabetes, obesity, poor anatomy, malnutrition). Or a "high risk incision" such as a foot and ankle incision, flap incision or major soft tissue resection with a large amount of dead space.

A healing complication is defined as the presence of at least one of these clinical scenarios: infection (superficial or deep), (evidenced by the prescription of oral antibiotics,(partial, superficial, or deep), or delayed healing (incision not 100% closed within 7 days of the first surgical procedure). Ongoing wound drainage from the incision after 96 hours, periwound erythema, minor dehiscence or major dehiscence.

The purpose of this study is to assess the efficacy of the FDA cleared device, Avance® Solo, an device that delivers negative pressure wound therapy to closed incisions (NPWTi), and to assess the number of healing complications that result from its use, compared to the current hospital standard Optifoam® Gentle Post op Dressing (a silicone backed foam that is conformable, with a border that is waterproof, flexible and breathable for increased comfort, with a wear time of up to seven days). This foam is currently stocked by the operating rooms at Mount Sinai hospital and indicated for use in high risk wounds (although there is no data to support its usage).

Historically, the use of negative pressure wound therapy for surgical incisions can assist in the management of surgical incisions. There are thought to be at least 6 positive mechanisms of action; protects the incision from the external environment, removes surface drainage and lymphatic drainage, resists gaping through application of lateral tension, increase breaking strength of healed incisions, reduces seroma and haematoma fluid collections, reduces edema, improves perfusion compared to area not treated with NPWT.

Many papers (primarily single center, single arm and or underpowered studies have supported the use of closed incisional NPWT. Previous basic science research has shown that NPWTi has a significant impact on improved incisional outcomes. Some have been small studies such as Pachowsky et al (2011) Nuremberg, Germany, who ultrasounded total hip arthroplasty: 9 patients with iNPWT in place for 5 days vs. 10 patients with standard dressings. He showed a reduction in volume of periwound seromas.

The largest study to date randomized the effect of NPWTi in 249 patient with 263 fractures. Groups were matched for different types of fracture. The average use of NPWT was for just 2.5 days and a statistically significant reduction in deep infection: 19.0 v 10.0% P = 0.049; and dehiscence was observed  $16.5 \text{ v} 8.6\% \text{ P} = 0.044.^4$ 

Please note for greater than 15 years there has been wide usage of the NPWTi by the investigator. The evidence supporting the theoretical use of this device is beyond the scope of this protocol.

# 1.2 OBJECTIVE(S)

The primary objective is to assess the frequency of a wound healing complication, in a closed incisional wound in a "high risk" surgical incision when treated with NPWTi versus a highly absorbent antimicrobial post – operative absorbent dressing. (HAAMPOD).

A healing complication is defined as presence of at least one of the following conditions: infection (superficial or deep), dehiscence (partial, superficial, or deep), or delayed healing (incision not 100% closed within 7 days of the first surgical procedure), drainage form the wound after 96 hours post operatively.

The secondary objectives are to assess any changes in the following assessments of the surgical incision weekly over the treatment period:

- Surrounding skin condition
- Incision complications, infection or clinical signs of infection
  - to assess the number and type of these complications individually including other postsurgical complications: skin necrosis, cellulitis, abscess, suture abscess, seroma, periwound edema or hematoma occurring within 21, 42, and 90 days postoperatively
- Pain during dressing changes

Assessment of the following at dressing changes:

- Duration/wear time
- Ease of use; difficulty with sleep
- Damage to surrounding skin on removal
- · Assessment of re-epithelialization/closure
- Patient comfort during wear; ease of ambulation
- Conformability of dressing
- Exudate management
- Reasons for removal

To assess the overall comparison of Avance® Solo to the HAMMPOD.

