# 3 EVALUATION PRODUCT(S)

# 3.1 DESCRIPTION OF EVALUATION PRODUCT(S)

Avance® Solo will include the collective description for a complete device capable of delivering negative pressure to the incision site and managing exudate generated by the incision. It comprises:

"This investigation pertains to Avance®Solo, a single use battery powered negative pressure system, with Mölnlycke as the legal manufacturer with its headquarter located in Gothenburg, Sweden. Avance®Solo consists of different products that are FDA compliant, which together form a system for wound management via the application of negative pressure (Figure 2). Avance®Solo maintains negative pressure nominally at -125 mmHg on low and moderately exuding wounds. The pump is pocket sized and can be carried in a pocket or attached to a belt with a belt clip that is assembled with the pump. To maintain the pressure, there is a recycling sound. To reduce the sound of cycling, a night case can be used to facilitate comfort during sleep."

A proprietary Controlled Fluid Management (CFM) technology, the Avance® Solo single use negative pressure system shares fluid management between an absorptive multi-layered dressing and a 50ml canister, reducing the potential for dressing saturation. This technology is theoretically designed to reduce the potential loss of therapy arising from dressing saturation.

 The addition of a canister to the absorptive dressing ensure the dressing does not become overwhelmed with draining and therapy will continue to be delivered regardless of dressing saturation

- Sharing fluid management between an absorptive dressing and canister can reduce the frequency of dressing changes
- Avance® Solo NPWT system continues to deliver negative pressure to the wound site, even with low to moderate amounts of fluid saturation in the dressing
- Avance® Solo features both audible and visual alarms so therapy can be restored in an efficient timely manner
- Avance Solo Border dressings Safetac® adhesive has been proven to minimise trauma to wound site and surrounding skin upon dressing removal
- -125mmHg continuous negative pressure

The pump is a controllable vacuum pump apparatus, which can be left to operate automatically, delivering continuous negative pressure (nominally -125mmHg) to the incision site. The pump's lifetime is 14 days and is powered with 2 lithium batteries specific to the pump. Batteries shall be replaced once pump alarms for Low battery or after 7 days.

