# 5.2 FURTHER POST OPERATIVE EVALUATION

The patient will be seen on day 21 ( $\pm$ 3), 42 ( $\pm$  5) and 90 ( $\pm$  7) at all time points the wounds will be assessed for:

Healing complications, defined as presence of at least one of the following:

- infection (superficial or deep)
- dehiscence (partial, superficial, or deep)
- delayed healing (incision not 100% closed within 7 days of the first surgical procedure).
- Ongoing wound drainage > 7 days post operatively

Secondary objectives are to assess the number and type of these complications individually including:

- wound drainage, type and amount;
- wound margin and periwound areas;
- and other aspects including but not limited to odor, pain, and need for debridement.
- skin necrosis, incisional pain, cellulitis, abscess, suture abscess, or hematoma occurring within 21, 42, and 90 days postoperatively.

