# At dressing removals the following information will be requested

- Dressing changed since last assessment (yes/no) (if yes how many times has the dressing been changed).
- Dressing in place (yes/no) obtain photograph
- Damage to surrounding skin (none, mild, moderate, severe)
- Level of damage to the reference wound on removal (none, slight, moderate, severe)
- Level of damage to the surrounding skin on removal (none, slight, moderate, severe)
- Condition of surrounding skin on removal (Healthy, fragile, inflamed, macerated, dry and flaky, other)
- Assess closure/ re epithelialisation of the incision
- Patient comfort during wear (Very comfortable, comfortable, acceptable, uncomfortable, very uncomfortable)
- Exudate level (None, slight, moderate, heavy)
- Assessment of infection (yes/no)
- Any incision complications and / or clinical signs of infection present (None, incision site static or deteriorating, dehiscence, increased exudate/secretion levels, increased pain, increased temperature around the wound, discolouration of granulation tissue, friable granulation, tissue necrosis, local erythema, oedema, purulent drainage, odour, other)
- Photographs (yes/no)
- Pain on removal of dressing (None, mild, moderate, severe)
- Reasons for removal (Dressing saturated, strike through, leakage, pain, Fell
  off, removed by patient, suture/staple removal, patients own request,
  inspection prior to patient discharge, other)
- Ease of use at this assessment (only at final removal)
- Occurrence of any product related adverse events will be documented at any point during the evaluation if required
- Is another dressing being applied at this assessment (yes / no?)

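### Drainage alone can make a patient a primary-endpoint event, but no common rule says how to read it while one arm is under suction and the other wears a passive foam

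*Combined protocol and SAP*

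**What the plan says.** **The component.** Section 1.2 defines a healing complication as any one of several conditions, among them "drainage form the wound after 96 hours post operatively". Section 1.1 words it as "Ongoing wound drainage from the incision after 96 hours", with the overall question being whether "surgical incisions develop healing complications within 21 days of surgery". Section 5.2 repeats the composite for the follow-up visits with a different limit: "Ongoing wound drainage > 7 days post operatively".

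**The test device.** Section 1.1 gives as one mechanism of negative pressure therapy that it "removes surface drainage and lymphatic drainage". Section 3.1 describes a pump "delivering continuous negative pressure (nominally -125mmHg) to the incision site" and a system that "shares fluid management between an absorptive multi-layered dressing and a 50ml canister". Section 5.1 allows at most two kits or two weeks of treatment.

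**The control.** Section 3.2 describes a silicone-faced foam with a superabsorbent core, worn for up to 7 days, with up to four dressings in 14 days. No suction or canister is described.

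**How fluid is recorded.** The Section 5.1 table places an incision assessment and photograph after each dressing removal and before the next application. The dressing-removal list in Section 6.1 has one graded fluid item, "Exudate level (None, slight, moderate, heavy". No rule links a grade to the composite. Section 5.2 adds visits on days 21, 42 and 90, where drainage type and amount are also noted. Section 2.1 states that the study is open label.

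**The concern.** The device acts directly on the quantity that this component measures. After the cut-off and until treatment stops, an assessor judging ongoing drainage in the device arm has three possible sources: the incision surface, the pad and the canister. In the control arm there are two: the surface and the foam. The definition does not choose among them, and the assessor knows the arm.

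The error could go either way. Fluid drawn into the pad or canister could be counted as ongoing drainage, which adds device-arm events. An incision recently cleared by suction could look dry, or a pad could look lightly loaded because the canister took part of the fluid; either removes device-arm events.

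The stake is the interpretation of the primary comparison. Section 8 presents the trial as a pilot meant to check the assumptions for a larger study, so its event rates by arm are its main product. If one component is read differently by arm, those rates partly reflect where the fluid is and not how the incision heals.

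**Working it through.** **1. The plan's own figure.** Section 8 gives 16% (or 5/30) v 8% (or 2/30), 80% power, alpha 0.05, and 162 per arm. For two proportions with pooled variance under the null, two-sided alpha assumed and no continuity correction:

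n = [1.960·√(2·p̄·(1−p̄)) + 0.842·√(p₁(1−p₁) + p₂(1−p₂))]² / (p₁−p₂)²

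- With 5/30 and 2/30: p̄ = 0.1167, and n = (0.890 + 0.377)² / 0.10² ≈ 161 per arm, against 162 stated.
- With 16% and 8%: n = 258 per arm.

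The stated size therefore rests on the counts, so the planned effect is best taken as 3 patients in 30, or 10 points. On the printed percentages it is 8 points, or 0.08 × 30 = 2.4 patients.

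**2. Overlap of the component with treatment.**

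- 96-hour cut-off: 14 − 4 = 10 of at most 14 treatment days lie after it.
- More-than-7-day cut-off: 14 − 7 = 7 of at most 14.
- Earliest follow-up visit: day 21 − 3 = 18, after the treatment maximum.

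The exposed period thus runs from the cut-off to day 14 at the latest. Drainage seen from the day-21 visit on is read off treatment in both arms.

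**3. Readings that the wording leaves open at a removal after the cut-off.**

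| What is read | Device arm | Control arm |
|---|---|---|
| Pad or foam only | Part of the fluid has gone to the canister | All absorbed fluid is in the foam |
| Pad plus canister | All fluid drawn by suction counts | Only passively absorbed fluid counts |
| Incision line, dressing off | May look dry after recent suction | Seen after passive absorption |

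Only the third uses the same source in both arms, and even there recent suction may leave a difference.

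**4. Illustration: device fluid counted as drainage.** The documents give no drainage rate, so the rates here and in step 5 are assumptions. A patient changes status only if no other component is present.

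- On counts: 2/30 + 3/30 = 5/30. Three of the 28 otherwise event-free device patients (10.7%), scored on drainage alone, remove the planned difference.
- On percentages, with a share f of the remaining 92% scored positive, the device rate is 0.08 + 0.92·f. At f = 5% it is 12.6%; at f = 8.7% it is 16.0%, equal to control; at f = 20% it is 26.4%.
- Two patients are 2/30 = 6.7 points, which is short of both 8 and 10.

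**5. Illustration: suction hides drainage.** Assume no true effect, 16% with other complications in both arms, and drainage as the only event in a share r of the remaining 84%. If a share m of those events is missed in the device arm, the spurious difference is −0.84·r·m.

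| r | m = 50% | m = 100% |
|---|---|---|
| 5% | −2.1 points | −4.2 points |
| 10% | −4.2 points | −8.4 points |
| 20% | −8.4 points | −16.8 points |

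Under either mechanism, some of the assumed values reach the planned 8 points. The documents do not show which values apply.

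**The case against.** The case against is substantial.

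- *The schedule already has the dressing off.* Section 5.1 puts the incision assessment after removal, Section 6.1 grades exudate at removal, and Section 5.2 repeats the composite off treatment. This stands, and it narrows the problem to on-treatment readings. But an exudate grade given at removal can still be taken from the pad, and Sections 1.1 and 1.2 do not limit the component to the later visits.
- *The definition already refers to the wound or incision.* It does, but canister fluid came from there too, so the wording does not exclude it.
- *Nobody is asked to inspect the canister.* This stands: the end-of-evaluation list asks only for the number used. Scoring from the canister is permitted by silence and not directed.
- *The control hides fluid too.* This stands. A reader might infer that the arms cannot be compared on drainage at all; the documents do not support that. The contrast is suction with a canister against passive absorption, during treatment only.
- *Fluid is not held for 14 days.* This stands. A reader might infer that it is, from the pump lifetime and the treatment maximum, but up to four dressings are supplied and nothing says that one pad or canister stays on throughout.
- *Components are assessed individually and the study is exploratory.* Separate counts do not give the composite without drainage, because patients can have several components. It could be derived from patient-level data, but the plan does not commit to it, and the source of the fluid cannot reliably be recovered later if it was not recorded. Being exploratory excuses low power, not a component read differently by arm.

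The missing exudate threshold affects both arms. It is a definition gap to close at the same time and not in itself evidence of device bias.

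**Conclusion.** The point holds for drainage scored between the cut-off and day 14 at the latest. In that period a component that alone decides the primary endpoint is read under suction in one arm and under a passive foam in the other, by assessors who know the arm and have no common rule.

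The direction and size of any bias cannot be determined from the documents. A reader might infer that the component must favour the device, or must count against it; neither follows. The illustration of three in 30 patients (10 points) takes the planned effect from the 5/30 and 2/30 counts and assumes that those patients have no other qualifying complication. Delayed closure at 7 days is in the same composite and may overlap with drainage, which would reduce the number of patients whose status depends on drainage alone.

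This should be settled before data collection. It does not invalidate the off-treatment assessments or the other components.

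**What to change.** In Sections 1.2 and 5.2, with matching wording in Section 1.1:

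1. Reconcile the 96-hour and more-than-7-day cut-offs so that the component has one definition.
2. Score drainage in both arms only as fluid seen at the incision line with the dressing off, at removals already planned and at the follow-up visits. State that pad and canister fluid does not count.
3. State which exudate levels on the removal form make it an event.
4. Report the composite with and without the drainage component, side by side, and note any conclusion that depends on that component.

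The cost is a sentence or two in the endpoint definition, one instruction on the removal form and one extra table. No visits or removals are added and treatment is unchanged.

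There are two downsides. Drainage between removals is not counted; because removal times are left to the clinician, the chances to observe it may still differ by arm. And reading at removal does not fully overcome masking by recent suction. The composite without drainage is needed for that reason: it shows how far the result rests on the component that the reading rule cannot fully equalise.

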#### 2 EVALUATION DESIGN

# 2.1 EVALUATION DESIGN

Open label, two armed, prospective, single center, quality equivalency assessment.

Immediate post operative application of Avance® Solo Negative pressure wound therapy on "high risk" closed surgical incisions. Versus the hospital best clinical practice dressing HAAMPOD. (Please note there is no prospective clinical data driven data, the hospital purchasing department develops and indicates the brand based upon cost).

The patient will be undergoing:

- Foot and ankle surgery
- Vascular groin incision, vascular axillary incisions
- Long leg vein harvest incision
- Closed forefoot and major amputation surgery
- Possibly: breast augmentation and reduction surgery

\*Note: The surgical indication is chosen based upon previously published data of high risk incisions. (It is beyond the scope of a protocol to educate the IRB in regards to the full definitions of high risk surgical inicisions)

Patients will participate in the study for 4 applications or up to 2 weeks treatment, whichever comes first. During this time clinicians will be asked to complete questions pertaining to the incision and to the performance and overall acceptability of Avance®Solo or the HAAMPOD.

Throughout the evaluation patients will be treated according to the product instructions for use for either product.

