#### 4.4 WITHDRAWAL

Any patient who interrupts the evaluation treatment for longer than 3 days will be withdrawn from the evaluation.

Patients who do not respond to therapy should be withdrawn from the evaluation only at the point where it becomes necessary to change the treatment on clinical grounds.

Patients may drop out or be withdrawn for the following reasons:-

- at their own request\*
- at the discretion of the clinician (because of lack of response, an adverse incident, poor compliance etc.).
- as their incision is no longer suitable for treatment with Avance® Solo
- \* Although patients need not give a reason for requesting withdrawal from the evaluation, the Clinician should make a reasonable effort to ascertain the reason(s), while fully respecting the patient's rights.

Patients who drop out or who are withdrawn from the evaluation will not be replaced if they have been entered onto the study and have received evaluation treatments.

Patients who drop out or who are withdrawn or whose wound heals will not be reentered into the evaluation at a later date.

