# 5 TREATMENT PLAN

# 5.1 TREATMENT REGIME

Patients will be informed of the evaluation requirements and asked to give informed consent prior to any evaluation activities taking place.

Patients meeting the eligibility criteria and agreeing to consent to their participation in this evaluation will receive treatment with Avance® Solo for a maximum of 2 kits or up to a maximum of 2 weeks treatment, whichever comes first. If randomized to HAAMPOD the patient will have a dressing applied per manufacturers guidelines. Up to 4 dressings will be applied over 14 days. Treatment will commence on Day 0 and dressing changes will take place as deemed necessary by the evaluation Clinician.

Avance® Solo should be applied in accordance with standard protocols and the product instructions for use.

The following table details the treatment regime for participation patients in the study.

Pre-Trial	Investigator discusses evaluation with the patient
	and provides the patient with a centre consent form

		for use of their data and photographs.
		Patient provides informed consent Complete eligibility checklist and medical history
±	First Dressing Application (Day 0)	Incision assessment Incision photograph First dressing application Video recording may be carried out
weeks Treatment	Second Dressing Application	First dressing removal Incision assessment Incision photograph Second dressing application Video recording may be carried out
Maximum of 2 we	Third Dressing Application	Second dressing removal Incision assessment Incision photograph Third dressing application Video recording may be carried out
Maxi	Fourth Dressing Application	Third dressing removal Incision assessment Incision photograph Fourth dressing application Video recording may be carried out
	Post Study	A patient interview may be carried out

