# At end of evaluation

- Reason for discontinuation (end of evaluation, wound closed, treatment interrupted for more than 3 days, Wound progressed sufficiently to warrant a change in treatment, patient withdrawn)
- Reason for patient withdrawal (product related adverse event, lack of response, poor compliance, patients own request, other)
- Overall acceptability of Avance®Solo to clinicians for indicated use (yes/no)
- Whether the clinicians were sufficiently satisfied with the following properties of the product overall in terms of:
- Exudate management
- Conformability
- Number of dressing changes, strips, pumps, canisters and batteries used
- Barrier to infection
- Condition of surrounding skin
- General (Ease of use, Dressing retention, durability, patient comfort & convenience)

- Pain on application of dressing (0-10 SCALE)
- Pain on removal of dressing (0-10 SCALE)
- Overall performance of dressing (1-5)
- Freedom from re-admission
- The use of post operative antibiotics
- The duration of post operative antibiotics if used

Comparison of Avance®Solo with HAAMPOD, whether the clinicians were satisfied with Avance®Solo compared to HAAMPOD:

- Exudate management
- Conformability
- Number of dressing changes
- Barrier to infection
- Condition of surrounding skin
- General (Ease of use, Dressing retention, durability, patient comfort & convenience)
- Pain on application of dressing
- Pain on removal of dressing
- Overall performance of dressing
- Use of post operative oral antibiotics

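### Sections 2.1, 4.4, 5.1 and 6.1 can be read as ending the study at closure, the fourth dressing or week 2, while Section 5.2 requires complication assessment at days 21, 42 and 90; the two are not reconciled.

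*Combined protocol and SAP*

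**What the plan says.** Several places in the protocol bear on when a patient leaves the study.

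**Text that points to an early end**

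- Section 2.1: "Patients will participate in the study for 4 applications or up to 2 weeks treatment, whichever comes first". The next sentence places data collection in the same period: "During this time clinicians will be asked to complete questions pertaining to the incision".
- Section 5.1: the table lists four dressing applications and then a post-study row, whose only content is "A patient interview may be carried out". It has no row for day 21, 42 or 90.
- Section 4.4: "Patients who drop out or who are withdrawn or whose wound heals will not be reentered into the evaluation at a later date". Healed patients are grouped here with those who have left.
- Section 6.1, end-of-evaluation list: "Reason for discontinuation (end of evaluation, wound closed, treatment interrupted for more than 3 days". Wound closure is thus one of the reasons for discontinuation. Freedom from readmission and the use and duration of postoperative antibiotics are collected on the same list. Section 6.1 has lists for baseline, dressing changes, dressing removals and end of evaluation, but none for the three later visits.

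**Text that requires longer follow-up**

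- Section 5.2: "The patient will be seen on day 21", and again around days 42 and 90, and "at all time points the wounds will be assessed for" a composite introduced as "Healing complications, defined as presence of at least one of the following".
- Section 1.1 frames the question over 21 days from surgery. Section 1.2 counts individual complications to 21, 42 and 90 days.
- Section 10.4 mentions follow-up and final-visit documentation, without saying who remains in follow-up or for how long.

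**The concern.** The protocol gives two answers to when a patient's participation ends, and the shorter one stops before any of the visits at which the composite is to be assessed. If a site followed the shorter one, a patient whose incision closed in the first week could be recorded as discontinued. An infection or reopening in the third week would then go uncounted.

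Three things would be at stake.

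- The 21-day question in Section 1.1 could not be answered from observation that stops by day 14.
- Time under observation would depend on healing and on dressing use. Section 3.1 says the device's shared fluid handling can reduce the frequency of dressing changes, so a stop defined by the number of applications could fall at different times in the two arms.
- Section 8 presents the study as a pilot to check the assumed complication rates. Rates taken from truncated follow-up would be too low for that purpose.

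Readmission and antibiotic use have the same problem if the end-of-evaluation form is completed at closure or at week 2. Antibiotic use matters in particular, because Section 1.1 treats a prescription of oral antibiotics as evidence of infection.

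**Working it through.** The plan states no figure for loss of late events, so there is none to reproduce. The sample-size figure in Section 8 does not enter this point. The check is a comparison of dates and then of endpoint components.

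**Step 1. Visit windows against the end of participation.** Under Section 2.1 participation ends at the latest at 2 weeks = day 14. Section 5.2 gives visit days and tolerances. A window opens at visit day − tolerance, and the gap is that day − 14.

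| Visit (Section 5.2) | Window | Gap after day 14 |
|---|---|---|
| 21 ± 3 | days 18 to 24 | 18 − 14 = 4 days |
| 42 ± 5 | days 37 to 47 | 37 − 14 = 23 days |
| 90 ± 7 | days 83 to 97 | 83 − 14 = 69 days |

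No visit window overlaps the participation period. The day 21 visit, which serves the Section 1.1 question, is also outside it.

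**Step 2. Which components are exposed.**

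- Delayed healing is defined by closure within 7 days of surgery, so it is settled before day 14.
- Prolonged drainage is defined by 96 hours in Section 1.2 and by 7 days in Section 5.2. Either threshold is passed before day 14.
- Infection and dehiscence have no such early cut-off and can arise after closure or after day 14. So can the individual complications of Sections 1.2 and 5.2, such as abscess, seroma or haematoma.

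The exposure is therefore to late infection and dehiscence in the composite, and to the secondary complications. A patient not closed by day 7 is already a composite event, so a later infection in that patient affects only the secondary counts.

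**Step 3. Weight of one missed event.** Section 8 expects 5/30 and 2/30 events. One event is 1/30 = 3.3 percentage points. Missing one in the control arm would turn 5/30 = 16.7% into 4/30 = 13.3%. Missing one in the device arm would turn 2/30 = 6.7% into 1/30 = 3.3%. This shows how sensitive the rates are to a single event. It does not estimate how many would be missed.

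**Step 4. Can the number missed be computed?** That would need the share of incisions closed by a given day, the rate of infection or dehiscence after that, and the share of patients whom sites would actually release early. The documents give none of these.

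**The case against.** The strongest reply is that follow-up is planned, and planned without condition. Section 5.2 says the patient will be seen at all three visits and makes no exception for healed or completed patients. Section 5.1 applies the same cap (two kits, which Section 6.1 gives as two dressings each, or two weeks) expressly to treatment, and its table is introduced as the treatment regimen. Section 2.1 itself speaks of two weeks of treatment. The bar on re-entry in Section 4.4 can mean only that nobody enrols twice. The reasons in Section 6.1 are options on a form, several of them about treatment, and not a rule cancelling visits. The study is also exploratory by its own description.

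Much of this stands. It makes treatment followed by follow-up the probable intent, and it rules out three stronger readings that a reader might infer.

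- *Healed patients will leave follow-up, so exit depends on outcome.* The documents do not establish this. It is a risk if Sections 2.1, 4.4 and 6.1 are followed literally.
- *A specific number of events will be lost.* The inputs are absent (step 4), and an estimate based on all closed incisions would partly recount patients who are already events under the day-7 rule.
- *Heavily draining incisions will use up four dressings before the day-7 closure check and escape it.* This fits poorly with Section 4.3.2, which excludes incisions needing daily inspection under the dressing. Drainage beyond 96 hours is also already an event under Section 1.2.

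The reply does not remove the contradiction. The design statement, the visit table and the data lists all omit visits that the endpoint section requires, and nothing says which governs.

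**Conclusion.** The point holds as an unreconciled contradiction, not as proof that visits will be skipped. Read literally, Section 2.1 ends participation at least 4, 23 and 69 days before the three follow-up windows open, and Sections 4.4 and 6.1 allow closure to be taken as the end of the evaluation. On that reading, infection, dehiscence and secondary complications arising after closure or day 14 can be missed, and the 21-day question is left unanswered. If every site follows Section 5.2 for every patient, nothing is lost. The size of any loss between these extremes cannot be computed from the documents. With so few events expected, even one missed event would move an arm's rate noticeably, so the wording should be corrected even in an exploratory pilot.

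**What to change.** - **Section 2.1:** make the cap apply to receiving study dressings instead of participating in the study, and state that participation lasts to the day 90 visit.
- **Section 5.1 table and Section 6.1 data lists:** add the day 21, 42 and 90 visits, with the complication items that Section 5.2 already names.
- **Sections 4.4 and 6.1:** state that wound closure or use of the fourth dressing ends dressing treatment only, and that a later reopening or infection counts as an event.
- **Section 6.1, end-of-evaluation items:** record readmission and antibiotic use through day 90 and not at the end of dressing treatment.

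None of this alters a dressing rule or the sample size. It adds no visit, since Section 5.2 already plans all three. The cost is protocol and questionnaire wording, plus the small burden of keeping healed patients on the existing visit list.
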